**iv. Time-to-event data**

Median observation time in each group and overall incidence rate up-to 180 days will be reported. Intervention group vs standard of care will be compared using Cox proportional hazards models with time to last assessment as offset (i.e. days between baseline and 1 year follow-up or last contact).

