## 2. Study objectives

### a. Primary objective

The aim of our study is to determine the safety and efficacy of an early goal-directed preload and afterload decrement with a target systolic blood pressure of 90 mmHg to 110 mmHg by aggressive vasodilatation versus standard medical care in a non-ICU setting in patients with acute HF. The primary endpoint is **death or heart failure re-hospitalization** up-to 180 days of follow-up.

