### **m. Intention- To -Treat (ITT)**

The intention to treat population consists of all patients randomized. The primary and secondary endpoints of patients randomized to early goal-directed decrement of preload and afterload (intervention group) will be compared to the patients randomized to standard of care by the intention-to-treat principle.

Patients without a follow-up assessment at 6 months for the primary endpoint will be censored at the time of the last follow-up information available.

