## **6. Statistical analysis**

### **r. General**

The general approach is to quantify the cumulative incidence of the composite primary endpoint using Cox proportional hazards models stratified by study centers and randomization factor as previously described.

Statistical analyses will be performed using SPSS / PC version 22.0 or higher and/or R version 3.4 or higher.

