**ii. Adjustments for covariates**

The primary analysis will be adjusted for four strong predictors of the composite primary endpoint (death or HF-rehospitalisation within 6 months): age, HF hospitalization in the year before inclusion, systolic blood pressure, and serum creatinine.

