22 Six days after admission or until discharge from the index hospitalization.

23 **iii. Dose of exposure and concentration**

- 24 – sublingual nitrates: 0.8 mg glyceryl trinitrate, sublingual, 3 times every ten minutes.
- 25 Sublingual nitrates have an approximate onset of action of 1-3 minutes and a half-life
- 26 of 1–4 min.
- 27 – hydralazine 25 mg p.o. four times a day (QID) for 2 days. Half-life, 2–8 hours,
- 28 – nitroglycerin patches in a dosage between 40 to 80 mg in 24 h depending on systolic
- 29 blood pressure and for 5 days. Elimination half-life takes around 10 minutes.
- 30

31

32

33 **9. Evaluation of patients at follow-up**

34 Patient are contacted at 90, 180 and 360 days follow-up (telephone calls, letters). During the  
35 FU patients will be asked about current medication, functional NYHA class and additionally,  
36 to complete Quality of life (EQ-5D-3L) and Kansas City Cardiomyopathy Questionnaire  
37 (KCCQ).

38 **aa. Follow-up at 90 days**

39 The follow-up 90 days months contains a self-reported medicament list update, potential  
40 endpoints assessment, a functional NYHA class assessment and Quality of Life (EQ-5D-3L)  
41 assessment.

42 **bb. Follow-up at 180 days**

43 The follow-up 180 days months contains a self-reported medicament list update, potential  
44 endpoints assessment, a functional NYHA class assessment and Quality of Life (EQ-5D-3L)  
45 and KCCQ assessment.

46 **cc. Follow-up at 360 days**

47 The follow-up 360 days months contains a self-reported medicament list update, a functional  
48 NYHA class assessment and Quality of Life (EQ-5D-3L) and KCCQ assessment.

49 .

50

51 **10. Evaluation of efficacy parameters**

52 **dd. Analysis of primary, secondary, and other efficacy endpoints**

53 **i. Analysis of primary endpoint**

54 The primary endpoint will be analyzed using survival analysis for cumulative incidence (e.g.  
55 Cox regression, Kaplan-Meier and Hazard Ratio) and log rank testing for significance at 180  
56 days.

57 **ii. Analysis of secondary endpoints**

58 Secondary endpoints will be analyzed using the same approach as for the Primary endpoints  
59 and interaction test (p-value) will be conducted between the treatment group and the sub-  
60 group variables.

61 **iii. Analysis of other endpoints**

62 All other endpoints, including novel biomarkers or neurohormones not yet specified in the  
63 protocol will be analyzed using the same approach as for the **Secondary endpoints**.

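### The SAP puts each patient's observed follow-up time into the Cox model as an offset, which exaggerates a true hazard ratio and understates its standard error

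*Combined protocol and SAP*

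**What the plan says.** The SAP section on time-to-event data opens with a 180-day report: "Median observation time in each group and overall incidence rate up-to 180 days will be reported". The next sentence compares the arms using "Cox proportional hazards models with time to last assessment as offset (i.e. days between baseline and 1 year follow-up or last contact"). It does not say whether the offset is in days or log days, or which event window the Cox model uses.

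Other parts of the SAP bear on the same model, and none mentions an offset:

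- **Primary objective:** the endpoint runs "up-to 180 days of follow-up".
- **Analysis of primary endpoint:** survival analysis ("Cox regression, Kaplan-Meier and Hazard Ratio) and log rank testing for significance at 180" days). Secondary endpoints follow the same approach.
- **General (statistical analysis):** "using Cox proportional hazards models stratified by study centers and randomization factor as previously described".
- **Adjustments for covariates:** "The primary analysis will be adjusted for four strong predictors of the composite primary endpoint".
- **Intention-to-treat:** "Patients without a follow-up assessment at 6 months for the primary endpoint will be censored at the time of the last follow-up information available".
- **Table 3:** an HR, confidence interval and p-value for each event endpoint. The footnote defines the primary endpoint as the first occurrence of either component.

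**The concern.** An offset is a term in the linear predictor whose coefficient is fixed at 1. Log exposure time is a proper offset in a Poisson or negative binomial model for counts. A Cox model has no need of it, because a patient contributes to the risk sets only while under observation.

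Here the term does harm. Time to last contact is observed after randomisation and ends early when the patient dies, so the model uses part of the outcome to predict the outcome. If treatment works, treated patients are followed longer and gain weight in the risk sets for that reason alone. The one-year span adds a mismatch: the primary comparison stops at day 180, but the offset would carry information from the following six months back into it.

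At stake are the Cox HR, confidence interval and p-value for the primary endpoint in Table 3, and the secondary endpoints analysed in the same way.

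**Working it through.** **Mechanism.** With offset o, an event in patient i contributes exp(βxᵢ + oᵢ) / Σⱼ exp(βxⱼ + oⱼ), summed over the risk set. The numerator's offset does not involve β. In the denominator each patient gets weight exp(oⱼ): the follow-up time itself if o is log time, or exp(days) if o is raw days. Patients about to die, or about to have their own event, get little weight.

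- With no treatment effect the weights are alike in both arms, so the HR stays centred on 1. But they depend on the future, and the model-based variance ignores this.
- With a true benefit the weights favour the treated arm. The expected treated share of events rises, and the observed shortfall looks larger than it is.

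**Inputs from the documents.** 770 patients, 385 per arm (protocol 8.3; SAP, Sample size); 1:1 allocation; two-sided 5% (protocol 8.2); 1–2% not assessable (2% used).

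**Inputs assumed.** The control event rate, the death share and the offset scale are not given.

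**The plan's own figure.** Read the 20% decrease as relative, from 50% to 40%:

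- HR = ln(0.60)/ln(0.50) = 0.511/0.693 = 0.737.
- Schoenfeld events = 4 × (1.960 + 0.842)² / (ln 0.737)² ≈ 31.4/0.0931, rounded up to 338.
- 338/0.45 = 751 patients, or 376 per arm. Freedman's formula gives 382 and two proportions 388.

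The stated 385 is therefore consistent with a control rate near 49–50%, though the documents do not confirm it. This motivates 50% as the main case.

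**Simulation, 180-day window.** Constant hazards, 50% control risk and 16% control mortality at 180 days. Death therefore makes up ln(0.84)/ln(0.50) = 0.174/0.693 = 25% of the hazard. Last contact ends at death, loss or day 360. Own time ends at first event, censoring or day 180. The last column is a check with 40,000 null trials per row (Monte Carlo error about 0.1 to 0.2 percentage points).

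| Offset | HR when truth is 0.737 | Type I error | Type I error, check |
|---|---|---|---|
| None | 0.737 | 5.1% | 4.7% |
| Log days to last contact | 0.717 | 6.8% | 6.4% |
| Log own time | 0.714 | 8.5% | 7.7% |
| Raw days to last contact | 0.685 | 9.4% | 9.3% |
| Raw own time | 0.667 | 16.6% | 16.4% |

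Under the null the mean HR was 1.00 in every row. The model SE stays at 0.102 (about 385 events; 2/√385 = 0.102), while the true SD with an offset is 0.110 to 0.145.

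**Sensitivity.**

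- *30% risk, 12% mortality:* 7.2–10.6% over the four offsets, but the no-offset model gave 6.4% in the same 2,000 trials, so the low end is partly noise. The 40,000-trial check gives 5.9%, 6.4%, 7.4% and 10.0%, against 4.8% without an offset.
- *Death as 40% of the hazard:* at 50% risk, 7.4–7.6% (log) and 12.5–15.8% (raw days); at 20% risk, 5.4% and 6.0–7.3%.
- *360-day event window, 20–55% risk at 180 days:* 5.1–12.8% (log) and 7.0–37.5% (raw days).

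**After the fix.** Without the offset, type I error was 4.3–5.2% at 180 days over the assumed event rates, and true HRs of 0.80 and 0.737 were recovered as 0.80 and 0.739–0.740.

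**The case against.** **The named significance test has no offset.** The SAP specifies "log rank testing for significance at 180" days, and the sample size rests on a log-rank test. This stands: that test keeps about 5%. A reader might infer that the primary significance test is inflated, but the documents do not support that. The Cox result still matters. It supplies the HR and interval in Table 3, and the covariate adjustment promised for the primary analysis needs a model such as Cox, since a plain log-rank test cannot provide it.

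**'Offset' may be loose wording.** The General, intention-to-treat and covariate sections, and the Table 3 footnote, describe an ordinary censored first-event Cox model. It would be wrong to say that the time-to-event section is the programmer's only guide, and a programmer who followed the other sections would introduce no bias. But the sentence fails on this reading too. If time to last assessment is the time variable, a patient re-hospitalised on day 30 and alive at one year is entered at about day 360, whereas time must stop at the first event.

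**The one-year span may serve the 360-day endpoint.** The section covers all time-to-event endpoints, so mentioning one year is not in itself an error. What is missing is a separate 180-day limit for the primary Cox comparison.

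**The size is not fixed.** This also stands. A reader might infer that type I error doubles. Raw days to last contact at 50% risk comes close, but log time does not at 180 days, and raw own time exceeds it. Values near 11% for log own time belong to a 360-day event window: 75% risk gives about 578 events and an SE of 2/√578 = 0.083, not the 0.102 of the primary window. Nor is the HR biased when there is no effect.

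**Conclusion.** The point holds as an instruction that is wrong as written. Taken literally, the offset exaggerates a true effect and makes the Cox interval and p-value too optimistic.

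At 180 days, with 50% control risk and 16% mortality, a true HR of 0.737 becomes about 0.72, 0.69 or 0.67, depending on how the offset is read. Cox type I error is about 6.5–8.5% (log time), 9% (raw days to last contact) or 16–17% (raw own time), against 5%. At 30% risk it is about 6–10%. The raw-days reading to last contact is closest to the SAP's wording.

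The direction follows from the mechanism. The size rests on assumed event rates, death share and offset scale, and on an unstratified, unadjusted simulation with constant hazards, whereas the SAP's model is stratified and adjusted. The damage is confined to the Cox HR, interval and p-value and to secondary endpoints analysed by the same approach. It does not reach the log-rank test.

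**What to change.** Replace the sentence in the SAP's time-to-event section with:

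> Time from randomisation to first event, censored at the last date known event-free and administratively at day 180 (day 360 for the 360-day endpoint); Cox model as in the general section (stratified, covariate-adjusted), without an offset.

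In the same edit, state whether the log-rank test or the stratified, adjusted Cox model is the primary test. If an exposure offset was meant for counts, move it to a count model as log follow-up time.

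The cost is one or two sentences. No data, sample size or endpoint changes, and the programming becomes simpler.

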**v. Ordinal scales and non-ordered scales data**

Ordered data will be reported as counts, compared Intervention arm vs Standard of care using chi-square tests for 2 x n tables with two-sided p-values.

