### **8.2 Statistical Analysis**

The statistical analyses will be performed using the SPSS / PC (version 14.0, SPSS Inc., USA) software package. A statistical significance level (p-value) of 0.05 will be used. All data will be analyzed on an intention-to-treat basis. Comparisons will be made using the t-test, Mann Whitney U-test, Fisher's exact test, survival analysis (Kaplan Meier method), Cox regression analysis and chi-square test as appropriate. All hypothesis testing will be two-tailed. Statistical support will be performed by [name] from the Institute of Social and Preventive Medicine of the University of Basel.

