### **f. Sample size**

Sample size calculation is based on the on the data from the BASEL V study. A hypothesized 20%-decrease of the composite endpoint death or HF re-hospitalization at 180 days, will require 385 patients per treatment arm to obtain, with a probability of 80%, a log rank test result that is statistically significant at the 5%-level. In order to compensate for an expected 1-2% of patients in whom the primary endpoint could not be assessed at 180 days due to loss to follow-up or complete withdrawal of ICF, it was planned to enroll approximately 780 patients.

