## h. Study assessments

The following study assessments are planned:

Study assessment schedule	Screening	D1	D2	D3	D4	D5	D6	Discharge	FU	D90	D180	D360
Screening of Patient in Emergency Department	S/I											
Check Inclusion/ Exclusion Criteria	S/I											
Inclusion: Patient signed the Informed Consent	S/I											
Inclusion: Randomize Patient in Secu Trial	S/I											
No inclusion: Enter Patient in " Screening Enrolment Log"	S/I											
HF assessment	S/I											
Measure vital signs 0h/ 30min/ 1h/2h/3h/4h/6h	S/I											
Give oral Capsule of Nitroglycerine (1)		I										
Apply the nitro patches according to the blood pressure		I										
Increasing nitro patches according to BP, stick for 24hrs (2)			I									
Reduction of nitro patches according to BP (2)			I	I	I	I						
Give one oral Hydralazine Tbl à 25mg every 6hours		I										
Collect Urine and Blood Samples		S/I	S/I	S/I			S/I					
Dyspnea Assessment		S/I	S/I				S/I	S/I				
Edema measurement		S/I					S/I					
Hand out the QOL and KCCQ Questionnaire				S/I						S/I	S/I	S/I
Collected the QOL and KCCQ Questionnaire					S/I					S/I	S/I	S/I
Actively search for AE's/ SAE's			S/I	S/I			S/I			S/I	S/I	S/I
Ask about Patient's Health status										S/I	S/I	S/I
Ask for medication										S/I	S/I	S/I
Ask about Dyspnea										S/I	S/I	S/I
Rehospitalization (3)										S/I	S/I	S/I

S= Standard group/ I= Interventions group

(1) every 10min x 3times

(2) target systolic BP  $\leq$ 110mmHg

(3) SAE, yes/no?

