**Table 4 Quality of Life assessments at Baseline and Follow-up**

80

81

Table 4 Quality of Life (EQ-5D-3L) assessments at Baseline and Follow-up

82

Mobility – mean score (±SD)	XX±XX	XX±XX	XX±XX	X.XX	XX±XX	XX±XX	XX±XX	X.XX	XX±XX	X.XX
Self-care – mean score (±SD)	XX±XX	XX±XX	XX±XX	X.XX	XX±XX	XX±XX	XX±XX	X.XX	XX±XX	X.XX
Usual activities – mean score (±SD)	XX±XX	XX±XX	XX±XX	X.XX	XX±XX	XX±XX	XX±XX	X.XX	XX±XX	X.XX
Pain/discomfort – mean score (±SD)	XX±XX	XX±XX	XX±XX	X.XX	XX±XX	XX±XX	XX±XX	X.XX	XX±XX	X.XX
Anxiety/depression – mean score (±SD)	XX±XX	XX±XX	XX±XX		XX±XX	XX±XX	XX±XX	X.XX	XX±XX	X.XX
Quality of life assessed at 180 days	N= xx	N= xx	N= xx		N= xx	N= xx	N= xx		N= xx	
VAS scale – mean score (±SD)	XX±XX	XX±XX	XX±XX	X.XX	XX±XX	XX±XX	XX±XX	X.XX	XX±XX	X.XX
Mobility – mean score (±SD)	XX±XX	XX±XX	XX±XX	X.XX	XX±XX	XX±XX	XX±XX	X.XX	XX±XX	X.XX
Self-care – mean score (±SD)	XX±XX	XX±XX	XX±XX	X.XX	XX±XX	XX±XX	XX±XX	X.XX	XX±XX	X.XX
Usual activities – mean score (±SD)	XX±XX	XX±XX	XX±XX	X.XX	XX±XX	XX±XX	XX±XX	X.XX	XX±XX	X.XX
Pain/discomfort – mean score (±SD)	XX±XX	XX±XX	XX±XX	X.XX	XX±XX	XX±XX	XX±XX	X.XX	XX±XX	X.XX
Anxiety/depression – mean score (±SD)	XX±XX	XX±XX	XX±XX	X.XX	XX±XX	XX±XX	XX±XX	X.XX	XX±XX	X.XX
Quality of life assessed at 360 days	N= xx	N= xx	N= xx		N= xx	N= xx	N= xx		N= xx	
VAS scale – mean score (±SD)	XX±XX	XX±XX	XX±XX	X.XX	XX±XX	XX±XX	XX±XX	X.XX	XX±XX	X.XX
Mobility – mean score (±SD)	XX±XX	XX±XX	XX±XX	X.XX	XX±XX	XX±XX	XX±XX	X.XX	XX±XX	X.XX
Self-care – mean score (±SD)	XX±XX	XX±XX	XX±XX	X.XX	XX±XX	XX±XX	XX±XX	X.XX	XX±XX	X.XX
Usual activities – mean score (±SD)	XX±XX	XX±XX	XX±XX	X.XX	XX±XX	XX±XX	XX±XX	X.XX	XX±XX	X.XX
Pain/discomfort – mean score (±SD)	XX±XX	XX±XX	XX±XX	X.XX	XX±XX	XX±XX	XX±XX	X.XX	XX±XX	X.XX
Anxiety/depression – mean score (±SD)	XX±XX	XX±XX	XX±XX	X.XX	XX±XX	XX±XX	XX±XX	X.XX	XX±XX	X.XX

83

84

85 It is expected that the Kansas city  
86 will be reported in secondary

87 **Figure 2 KCCQ summary change**

[figure not shown]
88

89

90

91

92

93

94

95

96

97

98

99

100

101 KCCQ summary score ranges from 0 to 100 with higher scores indicating better health status. An increase of 10 points or more from baseline  
102 corresponds to moderate or great clinical improvement.

103

104

105

106 It is expected that additional  
107 reported in secondary publications:

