**iii. Continuous scale data**

Continuous data will be compared Intervention arm vs Standard of care using Mann–Whitney U test with two-sided p-values.

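### Ordered scales are tested with an order-blind chi-square and continuous endpoints without their baseline value, and the first scheduled quality-of-life questionnaire falls on day 3

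*Combined protocol and SAP*

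**What the plan says.** **Ordered scales** (SAP 10.2.5, body heading ee.v): "Ordered data will be reported as counts, compared Intervention arm vs Standard of care using chi-square tests for 2 x n tables". The ordered measures collected are NYHA class (SAP 9), a five-category and a four-category dyspnoea item (Protocol 5, Patient-assessed Dyspnea), and the EQ-5D-3L dimensions. SAP Table 4 shows those dimensions as mean scores rather than counts.

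**Continuous data** (SAP 10.2.3, ee.iii): "Continuous data will be compared Intervention arm vs Standard of care using Mann–Whitney U test with two-sided p-values". No covariate is named. SAP 6.6.2 sets out covariate adjustment for the primary analysis only. SAP 2.2 defines BNP and creatinine as levels at 48 h and discharge, but dyspnoea and leg circumference as changes.

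**A second rule.** SAP 10.1.2 (dd.ii) sends secondary endpoints to the approach used for the primary endpoint: Cox, Kaplan–Meier and log-rank. SAP 10.2 assigns tests by data type. The two cannot both govern a BNP level or an NYHA class.

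**Quality of life.** In the SAP 3.5 schedule, the row "Hand out the QOL and KCCQ Questionnaire" has its first mark under D3, and the collection row has its first mark under D4. Neither row is marked at Screening, D1 or D2. Protocol 5 (Follow up) places the first questionnaire only somewhere in the initial hospitalisation. SAP Table 4 and Figure 2 report change from baseline, and the note to Figure 2 interprets "An increase of 10 points or more from baseline".

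**Status.** SAP 6.6.4 makes all secondary analyses explorative and reads their p-values without a threshold.

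**The concern.** A 2 x n chi-square gives the same answer if the category labels are shuffled. A treatment that moves patients one way along a scale is then tested on n − 1 degrees of freedom instead of one.

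Baseline blood is taken from every patient (Protocol 5, General Procedure for Both Groups) and BNP stratifies the randomisation (SAP 3.3). A comparison of follow-up levels alone leaves that information unused.

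The SAP synopsis expects faster relief of dyspnoea and a faster, larger fall in BNP. These tests would carry much of the evidence for both.

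The quality-of-life point is different in kind. By day 3 the arms have had 48 h of different open-label treatment. A score taken then is an outcome, and subtracting it removes whatever effect is already present.

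**Working it through.** **Plan's own figure.** No secondary endpoint has a stated power or sample size. The 385 per arm is for the primary endpoint: "will require 385 patients per treatment arm to obtain, with a probability of 80%, a log rank test result". It rests on "A hypothesized 20%-decrease of the composite endpoint death or HF re-hospitalization at 180 days", with no control rate given, so it cannot be reproduced directly. Read as a 20% relative reduction, it back-solves to a control rate of about 49–50%. It is used here only as the number per arm.

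**Inputs.** From the documents: 385 per arm; two-sided 5% (Protocol 8.2: "A statistical significance level (p-value) of 0.05 will be used"; "All hypothesis testing will be two-tailed"), used only as a yardstick since the SAP sets no threshold here; five dyspnoea categories. Assumed: category proportions, odds ratios, baseline correlations, and the share of the quality-of-life effect present by day 3.

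**1. Ordered scales.** Take control proportions p = 0.15, 0.25, 0.25, 0.20, 0.15. Multiplying the cumulative odds by 1.4 gives q = 0.1981, 0.2846, 0.2395, 0.1658, 0.1119. With m = (p + q)/2, the noncentrality is

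λ = 385 × Σ[(p − m)²/m + (q − m)²/m] = 6.87.

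Power at this λ is 53% on 4 df (chi-square) and 75% on 1 df (ordered test).

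| Common odds ratio | λ | 2 x 5 chi-square | Ordered test |
|---|---|---|---|
| 1.3 | 4.19 | 33% | 53% |
| 1.4 | 6.87 | 53% | 75% |
| 1.5 | 9.94 | 71% | 88% |

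Two simulations of 4,000 trials at odds ratio 1.4 gave 54% vs 75% and 52% vs 74%. More generally, where an ordered 1-df test has 80% power, the chi-square has 71%, 65% and 60% for 3, 4 and 5 levels. It then needs 23%, 39% and 52% more patients to reach 80%.

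**2. Continuous endpoints.** Let r be the correlation of baseline with follow-up, with equal SDs and variance 1 for the follow-up value. Variances are 1 (follow-up level), 2 − 2r (change) and 1 − r² (ANCOVA).

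- ANCOVA against level: 1 − r² = 0.75 at r = 0.5 and 0.51 at r = 0.7, a cut of 25–49%. A test with 60% power becomes Φ[(0.253 + 1.960)/√(1 − r²) − 1.960] = 72% and 87%.
- ANCOVA against change: (1 − r²)/(2 − 2r) = (1 + r)/2 = 0.75 and 0.85, a cut of 25% and 15%.

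Simulation with a 0.2 SD effect and 385 per arm:

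| r | Mann–Whitney, level | Mann–Whitney, change | ANCOVA |
|---|---|---|---|
| 0.5 | 78% | 77% | about 89–90% |
| 0.7 | 78% | 94% | 97% |

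The rank test itself costs little (relative efficiency 0.955 under normality). The loss comes from leaving out baseline.

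**3. Quality of life.** Let f be the share of the later effect already present on day 3. The change score estimates the fraction 1 − f of the effect. ANCOVA on the day-3 score estimates 1 − r·f. With the standard error held at the value that gives 80% power, power is Φ(fraction × 2.802 − 1.960).

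- f = 0: nothing is lost.
- f = 0.25: change keeps 75% of the effect, power 56%.
- f = 0.5: change keeps 50%, power 29%. ANCOVA on day 3 keeps 75% (r = 0.5, power 56%) or 65% (r = 0.7, power 44–45%).

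Adjusting for the day-3 score therefore does not cure the problem.

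**The case against.** The strongest reply is that the consequence is limited. No secondary endpoint is powered, all are explorative, and unadjusted Mann–Whitney is valid under randomisation and robust to skewed BNP. This stands: the cost is precision, and the primary endpoint is untouched. It does not excuse an order-blind test, because the SAP still reads each p-value as a measure of surprise, and explorative status does not remove bias.

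A reader might infer that the secondary endpoints as a whole ignore baseline. The documents do not support that. Many are events or times, to which neither test applies. Dyspnoea and leg circumference are defined as changes, and Tables 4 and 5 compare changes, so baseline is used there, only less efficiently. The 25–49% figure belongs to the level endpoints.

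A reader might also apply the 53% vs 75% comparison to the dyspnoea endpoint. Protocol 5 collects both a five-category item and a visual analogue scale, and neither document says which one defines the endpoint. If it is the visual scale, it already gets a rank test.

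Finally, one might conclude that the quality-of-life estimate is biased outright. No passage defines its baseline. Day 3 is inferred from a schedule that disagrees with the text elsewhere: hydralazine is marked on D1 only, against 48 h in SAP 8.1, and patch reduction starts on D2, against day 3 in Protocol 5. Those entries need reconciling too. The bias also requires a treatment effect by day 3. The inference is still sound, because both questionnaire rows line up with D90, D180 and D360 and no earlier mark exists.

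**Conclusion.** The point holds in three limited parts, plus a contradiction to resolve.

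- **Ordered scales.** The chi-square discards the order. At an odds ratio of 1.4 it has about 52–54% power against about 75% for a rank test. This rests on assumed proportions and on 385 per arm, which is an upper bound at follow-up because only surviving responders have an NYHA class. It applies to NYHA class, and to the five-category dyspnoea item if that is used.
- **Continuous endpoints.** Baseline adjustment would cut variance by 25–49% for BNP and creatinine levels and by about 15–25% for change endpoints, at an assumed correlation of 0.5–0.7. This is an efficiency gain; the planned test is not invalid.
- **Quality of life.** If day 3 is the first measurement, change from it is biased in proportion to the effect already present. If it is not, this part falls away.
- **Method.** SAP 10.1.2 and SAP 10.2 conflict on how secondary endpoints are analysed.

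The changes are worth making before analysis, but none bears on the primary result.

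**What to change.** 1. Reconcile SAP 10.1.2 with SAP 10.2: list each secondary endpoint with its data type and its one method, and state which dyspnoea measure defines the dyspnoea endpoint.
2. Ordered scales: replace the 2 x n chi-square with a Wilcoxon test or a proportional-odds model.
3. Continuous endpoints: ANCOVA on the follow-up value, with the pre-randomisation value and the randomisation strata as covariates. Use the log scale for BNP and creatinine and report geometric mean ratios. Keep Mann–Whitney as a sensitivity analysis.
4. EQ-5D and KCCQ: state when the first questionnaire was completed. If it was day 3, compare the 180- and 360-day scores directly between arms, neither subtracting nor adjusting for the day-3 score, and relabel that column of Table 4 and the reference point of Figure 2 as day 3.

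The cost is SAP wording and slightly more modelling. No new data are needed.
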